1.3 Schedule of activities

The SoAs provide an overview of the protocol visits and procedures. The investigator may schedule visits (unplanned visits) in addition to those listed in the SoAs, in order to conduct evaluations or assessments required to protect the wellbeing of the trial subjects.

Activity		Visit 0	Visit 1	Visit 2	Visit 4	Visit 5	Visit 6 ^k	Visit 7 ^k	Early termination
W	eek(s)			1	4	7	12	26	
	Day	-30 to -1	1	8+2	29±7	50±7	85±10	182±20	
		(Screening)	(Day of inj. 1; pre-dose except IMP injection)	(~7 d post inj.)	(~28 d post inj.)	(~49 d post inj.)	(~84 d post inj.)	(~181 d post inj. EOT Visit)	
Collect informed consent		Х							
Assess inclusion/exclusion criteria compliance		Х	X (review)						
Collect demographic and medical history		Х	X (update)						
Physical examination		Х	X a	X a	X a			X a	X a
Vital signs, body weight ^b		Х	Хc	Х	Х			х	Х
Urine pregnancy test for WOCBP		Х	х					х	х
Urine for clinical laboratory ^d		Х	х		Х			х	х
Blood draws for clinical laboratory (15 mL) ^e		Х	х		Х			х	Х
Allocation and randomization to IMP			х						
IMP injection, then observe subjects for ~1 h			х						
Subject hotline availability		Start	=>	=>	=>	=>	=>	End	(End)
Oral swabs for NAAT-based SARS-CoV-2 for screen	ing ^f	Xg	X a						
Oral swabs for NAAT-based SARS-CoV-2 for surveill	ance			Х	Х	Х	Х	х	х
Oral swabs for SARS-CoV-2 sequencing ^h		Xg	Хa	Х	Х	Х	Х	х	х

Table 1: Schedule of events for Group A (with one injection of either Comirnaty or BNT162b2s01)

Activity	Visit 0	Visit 1	Visit 2	Visit 4	Visit 5	Visit 6 ^k	Visit 7 ^k	Early termination
Week(s)			1	4	7	12	26	
Day	-30 to -1	1	8+2	29±7	50±7	85±10	182±20	
	(Screening)	(Day of inj. 1; pre-dose except IMP injection)	(~7 d post inj.)	(~28 d post inj.)	(~49 d post inj.)	(~84 d post inj.)	(~181 d post inj. EOT Visit)	
Blood draws for NATAB and nucleocapsid protein testing (15 mL)		х	х	Х		Х	х	х
Blood draws for CMI (120 mL each)		Х	Х			Х	х	Х
Issue/collect subject diaries		X (issue)	X (collect)					
Subjects report daily reactogenicity (incl. body temperature) in their diary on Day 1 and for 7 d post each vaccination		X (post- dose) ^j	х					
Record AEs since last visit		х	Х	Х	Xi	Xi	Xi	X ⁱ
Record pregnancies		Start	=>	=>	=>	=>	End	(End)
Record concomitant medication		Х	Х	Х	XI	XI	XI	XI

Note: The SoA allows for ad hoc SARS-CoV-2 testing for symptomatic or asymptomatic subjects.

a Brief (symptom-directed) physical examination; no height measurement.

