3 OBJECTIVES AND ENDPOINTS

OBJECTIVES	ENDPOINTS	
Primary objectives	Endpoints	
To determine the safety and tolerability of one or two boosting doses of Comirnaty or one dose of BNT162b2s01 in BNT162-01 trial subjects, or two boosting doses of Comirnaty in BNT162-04 trial subjects.	 For all Group A and Group B subjects: The proportion of subjects in each treatment group with at least one SAE or the proportion of AESIs occurring up to 26 weeks after the first IMP injection. For Group A and a selected subset of Group B subjects: The frequency of solicited local reactions (pain, tenderness, erythema/redness, induration/swelling) at the injection site recorded up to 7 d after each IMP injection. The frequency of solicited systemic reactions (vomiting, diarrhea, headache, fatigue/tiredness, fever, chills, nausea, new or worsened muscle pain, new or worsening joint pain) recorded up to 7 d after each IMP injection. The proportion of subjects with at least one unsolicited TEAE occurring up to 28 d after IMP injection in each treatment group. 	
Secondary objectives	Endpoints	
To describe changes in SARS-CoV-2 neutralizing antibody titers from baseline to reference and SARS-CoV-2 variant B.1.351.	 For Group A and Group B subjects (except transplant subjects): Antibody titers to recombinant S1 and RBD protein derived from reference and SARS-CoV-2 variant B.1.351** will be assessed at baseline (Day 1) and then Day 8, Weeks 3*, 4, 7*, 12, and 26: Neutralizing antibody titers. Antibody titers (ELISA). SARS-CoV-2 functional cross-neutralization of variant B.1.351** to reference strain. *Group B only **Group B transplant subjects only: Antibody titers to recombinant S1 and RBD protein derived from SARS-CoV-2 will be assessed at baseline (Day 1) and then Day 8, Weeks 4, 12, and 26 post Dose 1, and at Dose 2 (Day 1) and then Day 8, Weeks 4, 12, and 26 post Dose 2: Neutralizing antibody titers. Antibody titers (ELISA). 	
Exploratory objectives	Endpoints	

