8.3.1 Time period and frequency for collecting AE, AESI, and SAE information

For trial subjects enrolled in this clinical trial, i.e., after transfer from the parent trial to this trial, all AEs, AESI, and SAEs (including a death) will be recorded at the time points listed in the SoA in Section 1.3. All safety reporting will occur through this rollover trial; this includes the reporting of non-vaccine related AEs that are unresolved from the parent trial.

For subjects who receive a non-trial SARS-CoV-2 vaccination, AEs/SAEs will be collected as specified above until the date when the subject was vaccinated with the non-trial SARS-CoV-2 vaccine. The AEs expected to be captured after non-trial SARS-CoV-2 vaccination are within the frame of post-marketing safety data reporting.

Investigators are not obligated to actively seek AEs or SAEs at any time after a trial subject has been discharged from the trial, however, if the investigator learns of any SAE (including a death), that they consider to be reasonably related to the IMP administration or trial participation, the investigator must promptly notify the sponsor.

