10.3.1.10 Reporting of SAEs and AESIs

All SAEs and AESI (even if the AESI is non-serious) which occur in a trial subject during the observation period, whether considered to be associated with trial medication or not, must be reported by the investigator to the sponsor within 24 h following knowledge of the event.

All SAEs occurring after the end of the observation period only have to be reported to the sponsor if the investigator suspects a relationship to trial medication or the trial procedure.

SAE and AESI reporting to sponsor

For the period of observation, see Section 8.3.1.

For any SAE or AESI (even if the AESI is non-serious), the investigator needs to complete the applicable paper Report Form which must be sent to the sponsor via one of the following reporting methods:

- Safety Report Fax No.:
- Safety Report Email Address:

Information for final description and evaluation of a case report may not be available within the required time frames for reporting. Nevertheless, for regulatory purposes, initial reports should be submitted if the following minimal information is available:

CCI

- An identifiable trial subject (trial subject number)
- A suspected medicinal product
- An identifiable reporting source (investigator/trial site identification)
- An event or outcome that can be identified as serious

All SAE/AESI follow-up information should be sent to the sponsor (indicating that this is a "follow-up" report using the SAE Form or the Additional Information and Follow-Up Form) without delay as described above and accompanied by appropriate anonymous supporting documentation (e.g., discharge letters, medical reports or death certificates), until a final outcome and date are available. All confidential information (name, address, full day of birth) needs to be blackened before sending. In addition to a medical record, the investigator should complete an Additional Information and Follow-Up Form, which contains the SAE term and trial subject number.

A copy of the submitted SAE/AESI report must be retained on file by the investigator. If explicitly required according to national legislation, the investigator must submit copies of the SAEs to the IEC or authority and retain documentation of these submissions in the ISF.

In case an investigator or any other trial team member has questions on safety reporting the sponsor may be contacted via: Email: CCI

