6.1.1. Tables and listings

Tables

In general, data will be summarized as follows:

- Group A by vaccine [Comirnaty[®], BNT162b2s01], and total
- Group A subjects having received Comirnaty[®] by HIV infection status
- Group A subjects having received BNT162b2s01 by HIV infection status
- Group B by transplant status, and total
- Group B immunology subset by transplant status, and total

Descriptive summary tables and figures will be based on scheduled visits.

Continuous variables will be summarized using the following descriptive statistics: number of subjects with non-missing data (n), mean, standard deviation (SD), median, minimum (min) and maximum (max).

Descriptive statistics of titer and fold rise of titer will additionally include geometric mean and its two-sided 95% confidence interval (CI). The geometric mean titer (GMT) is calculated as the mean of the logarithm of the functional antibody titers, backtransformed into the original scale. Two-sided CIs will be obtained by calculating CIs using t-distribution for the mean of the logarithmically transformed assay results and transforming the limits back to the original scale.

Geometric mean fold rise (GMFR) is calculated as the mean of the difference of logarithmically transformed assay results (post vaccination time point – pre vaccination time point) and back-transformed into the original scale. Two-sided CIs will be obtained by calculating CIs using Student's t-distribution for the mean difference of the

logarithmically transformed assay results and transforming the limits back to the original scale.

Categorical variables will be summarized presenting absolute and relative frequencies (n and %) of subjects in each category (including the category 'missing' if applicable). Percentages will be calculated based on the number of subjects in the respective analysis set (N) as denominator if not stated differently. Percentages may be presented with exact 95% Clopper-Pearson CIs.

SDs and CIs will only be calculated if values from at least 3 subjects are available.

Listings

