6.1.3. Missing data

As a general rule, missing data will not be imputed (i.e., missing data will not be replaced but will be handled as "missing" in the statistical evaluation), with the following exceptions for summary analyses:

Clinical safety laboratory variables given as "<xx" will be evaluated as 0.5*xx in the summary tables. In the listings they will be displayed as "<xx" or similar.

Data values below lower limit of quantification (LLOQ) or detection (LLOD) will be imputed with 0.5*LLOQ or 0.5*LLOD, respectively, for the analysis of continuous data. Values above the upper limit of quantification (ULOQ) or detection (ULOD) will be imputed with 2*ULOQ or 2*ULOD, respectively, for the analysis of continuous data. In the listings they will be displayed as "<xx" or ">yy" as appropriate. In the tables they will be displayed as "<LLOQ"/("<LLOD" or ">ULOQ"/(">ULOD" in descriptive statistics (e.g., in mean, median, min, max) as appropriate. A footnote will be added to show the value of LLOQ or LLOD or ULOQ or ULOD.

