6.4. Primary endpoint analyses

The primary endpoints are solicited local reactions at the injection site occurring up to 7 days after each injection, solicited systemic reactions occurring up to 7 days after each injection, the proportion of subjects with at least one serious adverse event (SAE) occurring up to 26 weeks after the first injection, the proportion of subjects with at least one adverse event of special interest (AESI) occurring up to 26 weeks after the first injection and the proportion of subjects with at least one unsolicited treatment emergent adverse event (TEAE) occurring up to 28 days after each injection.

All primary analyses will be performed using the SAF and analyses of adverse events for Group B will possibly be repeated using the SAFB.

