6.4.3. Adverse events

Definition

For detailed information on adverse events see Section 10.3 of the protocol. Solicited AEs that are recorded from the subject diaries on the reactogenicity CRFs will not be reported as AEs unless the solicited AE meets criteria for SAE or begins after Day 8 or started before Day 8 and continues past Day 8.

Adverse events (AEs) will be coded using the Version MedDRA[®] 24.0 to get a system organ class (SOC) and preferred term (PT) for each AE.

A TEAE is defined as any AE with an onset after the first injection (Dose 1) (if the AE was absent before the first injection) or worsened after the first injection (Dose 1) (if the AE was present before the first injection (Dose 1)). AEs with an onset date more than 28 days after the last injection will be considered as treatment emergent only if

assessed as related to IMP by the investigator. AEs that cannot be determined to not be treatment emergent due to missing date or time will be defined as TEAE.

Note: To clarify the definition in the protocol, AEs with an onset date at the date of the first injection (Dose 1) will only be considered as treatment emergent if the AE occurred after the first injection (Dose 1). AEs with missing time and occurring on the day of Dose 1 or AEs with missing date will be analyzed as treatment emergent.

TEAEs will be evaluated for following time interval and groups:

- Up to 28 days after the first IMP injection (Group A and immunology subset of Group B)
- After the first IMP injection up to 28 days after the second IMP injection (immunology subset of Group B non-transplant)
- After the second IMP up to 28 days after the second IMP injection (immunology subset of Group B transplant)
- All TEAEs (Group A and immunology subset of Group B)

AEs are assigned to the time interval according to their start date and time. AEs with missing date will be assigned to each of the respective intervals if it cannot be ruled out, that it belongs to the time interval.

Adverse events of special interest (AESIs)

The following events will be reported as AESIs: myocarditis, pericarditis, anaphylaxis, thromboembolic events (e.g., deep vein thrombosis, stroke, myocardial infarction), immune thrombocytopenia and immune based neurologic events (e.g., optic neuropathy, Guillain-Barré syndrome). AESIs are recorded in the CRF.

AESIs and SAEs will be evaluated up to 26 weeks after the ICF was signed for all groups.

Analysis

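### The Visit 7 window lets compliant subjects leave up to 20 or 21 days before the 26-week primary SAE/AESI period ends, with a small downward bias

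*Protocol*

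**What the plan says.** **Endpoint.** Protocol Section 3 gives, for all Group A and Group B subjects, a primary endpoint of SAEs and AESIs "occurring up to 26 weeks after the first IMP injection". SAP Section 6.4 repeats the anchor: "the proportion of subjects with at least one serious adverse event (SAE) occurring up to 26 weeks after the first injection". Both count any SAE, related or not.

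**Last visit.** Visit 7 is the end-of-trial visit in Tables 1, 2 and 3 of protocol Section 1.3, at Day 182±20 from injection 1. Table 1 describes it as "181 d post inj. EOT Visit". The subject hotline ends at that visit. Under Section 4.4, a subject who has made all planned visits is a completer.

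**After the last visit.** Protocol Section 8.3.1 states: "Investigators are not obligated to actively seek AEs or SAEs at any time after a trial subject has been discharged from the trial". The same sentence keeps a duty to notify the sponsor of any SAE that the investigator learns of and considers reasonably related. Section 10.3.1.10 is consistent with this: "All SAEs occurring after the end of the observation period only have to be reported to the sponsor if the investigator suspects a relationship". Section 10.3.1.8 says the same for events after discharge.

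**Analysis.** SAP Section 6.1.1: "Percentages will be calculated based on the number of subjects in the respective analysis set (N) as denominator if not stated differently". SAP Section 6.1.3: "As a general rule, missing data will not be imputed". For this endpoint the SAP gives no person-time or time-to-event method and no minimum follow-up.

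**A second anchor.** SAP Section 6.4.3 states: "AESIs and SAEs will be evaluated up to 26 weeks after the ICF was signed for all groups". That is a different start point from protocol Section 3 and SAP Section 6.4.

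**The concern.** The endpoint promises 26 weeks of SAE and AESI ascertainment, but the schedule lets a site close a subject's follow-up after 23 weeks (161 days) with no protocol deviation. An unrelated hospitalization on Day 170, in a subject discharged on Day 162, falls inside the endpoint period, yet no rule requires anyone to ask about it or report it. Nothing would mark that subject as incompletely followed.

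This is the only primary endpoint that covers all subjects; the reactogenicity and unsolicited TEAE endpoints are limited to Group A and a subset of Group B. Because the endpoint is capped at 26 weeks, late visits cannot offset early ones. For rare events, a single missed case changes the reported proportion.

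**Working it through.** **Day count.** Table 1 makes Day 1 the injection day, so days after injection = study day − 1. This reproduces the table's own labels: Days 8, 29, 50, 85 and 182 give 7, 28, 49, 84 and 181.

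**Gap for one subject.** The endpoint period is 26 × 7 = 182 days. Gap = max(0, 182 − (visit day − 1)).

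| Visit 7 held on | Days after injection | Gap |
|---|---|---|
| Day 162 (earliest) | 161 | 21 |
| Day 182 (nominal) | 181 | 1 |
| Day 183 | 182 | 0 |
| Day 202 (latest) | 201 | 0 |

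Worst case: 21/182 = 11.5%.

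**Alternative count.** SAP Section 6.4.1 treats the 7-day diary interval as study days 1 to 7. By analogy, 26 weeks would be study days 1 to 182, and the worst case is 182 − 162 = 20 days (11.0%).

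**Average gap.** Assume visits are spread evenly over the 41 days from 162 to 202. On the schedule's count the gaps sum to 1 + 2 + … + 21 = 231, so the mean is 231/41 = 5.6 days, and 5.6/182 = 3.1%.

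**Consent anchor of SAP Section 6.4.3.** Consent falls between Day −30 and Day −1. With consent on Day −d, the period ends on study day 183 − d, that is between Day 153 and Day 182. The gap after a Day 162 visit is max(0, 21 − d): 20 days for consent on Day −1, and none for consent on Day −21 or earlier.

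**Who is affected.** Transplant subjects given injection 2 finish at Visit 12, Day 182±20 after that injection, which is given 3 to 7 months after injection 1. At the SAP's 30.25 days per month, the shortest follow-up is 3 × 30.25 + 161 = 251.75 days after injection 1, so they have no gap. At the planned maxima, 90 + 459 − 15 = 534 non-transplant subjects remain. A transplant subject who does not receive injection 2 and ends at Visit 7 is also affected.

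**Effect on the proportion.** The documents give no expected SAE rate, so the 26-week risk p is an assumption. With a constant hazard, and every subject seen on Day 162 (the extreme case), observed risk = 1 − (1 − p)^(161/182).

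| Assumed p | Observed | Difference (points) | Missed of 90 | Missed of 534 |
|---|---|---|---|---|
| 0.5% | 0.442% | 0.058 | 0.05 | 0.31 |
| 1% | 0.885% | 0.115 | 0.10 | 0.61 |
| 2% | 1.771% | 0.229 | 0.21 | 1.22 |
| 5% | 4.436% | 0.564 | 0.51 | 3.01 |

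With visits evenly spread, the relative loss is about 3.1%. At p = 1% that is 0.031 points, or 0.00031 × 534 ≈ 0.17 subjects, and 0.00031 × 90 ≈ 0.03 in Group A.

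**The case against.** A tolerance around a nominal Week 26 visit is ordinary practice, and this trial is descriptive: no hypothesis, no sample-size calculation, no testing. The window is the same in both randomized arms. The SAP prints percentages without decimals, so at an assumed 1% risk even the extreme case (0.885%) prints as 1%. All of this stands, and it limits the weight of the point.

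A reader might infer that every one of the 549 planned subjects loses 21 days. The documents do not support that. The figure 549 is a maximum, transplant subjects given injection 2 are followed well past 26 weeks, and 21 days is the earliest permitted visit on one of two day counts. Under the consent anchor 21 days cannot occur.

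A reader might also take the gap as wholly unobserved. That is too strong, because related SAEs that the investigator learns of must still be reported. What is lost is chiefly unrelated events. Counting the subject as event-free is likewise an inference from the denominator and no-imputation rules; no sentence says so.

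Finally, the downward direction depends on cutting events at 26 weeks. The general AE and SAE summaries in SAP Section 6.4.3 state no cut-off of their own. If they tabulate everything recorded, late visits add events and the one-sidedness does not carry over. It holds for the primary endpoint as protocol Section 3 and SAP Section 6.4 define it.

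Dropout, and the exclusion of data after a non-trial vaccination, can shorten observation by more. They do not justify a shortfall that the schedule permits in fully compliant subjects.

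**Conclusion.** The mismatch is real but modest. For Group A, and for Group B subjects whose last visit is Visit 7, the schedule permits discharge up to 20 or 21 days (at most 11.5%) before the primary SAE/AESI period closes. Collection of unrelated events then lapses, and the planned analysis does not adjust for it. The mean shortfall of 5.6 days (3.1%) assumes evenly spread visits; translating it into missed subjects also assumes a constant hazard and a chosen event rate. The bias in the endpoint as defined is downward only.

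Nothing here supports a claim that the safety conclusions would be materially wrong or that the comparison between randomized arms is distorted. The case for acting is that the shortfall is avoidable at low cost. The conflict between the consent and injection anchors is a separate inconsistency, but it determines how large the gap is, so the two should be settled together.

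**What to change.** 1. Keep Day 182±20 for Visit 7 procedures and sampling. A one-sided window starting at Day 183 would make the nominal Day 182 visit a deviation and shift the Week 26 antibody and CMI samples.
2. Add a footnote to Tables 1, 2 and 3: if Visit 7 takes place before Day 183, the site telephones the subject on or after Day 183 to ask about SAEs and AESIs. Discharge and the end of the observation period are deferred to that call. It is not needed for transplant subjects who go on to injection 2.
3. Align the hotline row, which now ends at Visit 7, and protocol Sections 8.3.1 and 10.3.1.10. The hotline is a line that subjects call, so it does not replace a site-initiated query. Remote collection by telephone already has a precedent in the Table 1 footnote on non-trial vaccinations.
4. Reconcile SAP Section 6.4.3 with protocol Section 3 and SAP Section 6.4, so that one anchor and one cut-off apply to this endpoint.

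Cost: one short call per early attender. If visits are evenly spread, 21 of the 41 permitted days fall before Day 183, so about 534 × 21/41 ≈ 274 calls at the planned maximum.
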